Enrolled participants were randomly divided into probiotics group or placebo group. Seventeen and 19 participants were respectively assigned to the placebo group and the probiotics group. The probiotics we used were in the form of 100mg L. bulgaricus powder packets, each containing 1×10^8 CFU of probiotics (TCI CO., Taipei, Taiwan). Initially (day 1), participants underwent measurements for weight, body fat, and BMI, and fasting blood

[figure not shown]
IRB/REC No. :	CMUH110-REC2-070
Page No. :	5/28

samples were collected. Subsequently, each participant received one package of either probiotic or a placebo sample, along with drinking water on the same day. From that point onward, participants self-administered one package of the sample daily for 12 weeks and the participants' sample consumption and physical conditions were tracked by the research assistants weekly. Throughout the study duration, participants maintained their regular diet and lifestyle. At the endpoint (day 84), weight, body fat, and BMI were measured, and fasting blood samples were collected again. Weight and body fat were measured with Karada Scan 216 (OMRON, Kyoto, Japan). Alanine aminotransferase (ALT), aspartate aminotransferase (AST), blood urea nitrogen (BUN), creatinine (CRE), CHOL, HDL-C, LDL-C, TG, hemoglobin A1c (HbA1c), and Glucose-Ante Cibum (Glu-AC) levels were analyzed and reported by Laboratory Medicine in Chinese Medical University Hospital (Taichung, Taiwan). Data were expressed as the mean \pm standard error of the mean (SEM). Statistical significance between groups were done by student paired t-test or Mann-Whitney test. P-values lower than 0.05 were considered statistically significant.

Data Analysis:

The statistical analysis was conducted using GraphPad's unpaired independent samples t-test, with significance set at $*P < 0.05$.

Flow Diagram of the study:

Group	Placebo		Probiotics	
	Mean	SD	Mean	SD
Age, years	41.38	12.71	41.56	10.92
Gender, male/female	7/6		12/6	
Weight, kg	78.69	15.64	80.77	15.11
Body fat, %	32.08	6.65	30.84	5.26
BMI	29.32	5.40	28.89	3.59
ALT, U/L	26.00	15.37	32.63	18.96
AST, U/L	21.45	10.62	23.36	7.44
BUN, mg/dL	13.10	2.69	13.67	2.94
CRE, mg/dL	0.80	0.14	0.83	0.15
CHOL, mg/dL	182.18	43.04	201.60	40.97
HDL-C, mg/dL	46.82	5.82	48.50	16.26
LDL-C, mg/dL	122.82	42.15	111.01	30.40
TG, mg/dL	139.62	52.18	220.94	173.92
HbA1c, %	5.80	0.83	6.17	1.07
Glu-AC, mg/dL	93.45	16.92	109.06	34.13

Table 1: Analysis of Baseline Values of the Participants

Results

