
[figure not shown]

Figure 1: Changes in Body Composition

Placebo represents the placebo control group, and Probiotics represents the probiotics experimental group. The changes in body weight (A), body fat (B), and BMI (C) before and after consumption were calculated and expressed as a percentage of the initial values. No significant differences were observed between the two groups.

[figure not shown]

Figure 2: Changes in Blood Sugar Indices

Placebo represents the placebo control group, and Probiotics represents the probiotics experimental group. The changes in fasting blood glucose (GLU-AC) before and after sample consumption (A) and changes in glycated hemoglobin (HbA1c) expressed as a percentage of the initial values (B) were calculated. No significant differences were observed

between the two groups.

[figure not shown]

Figure 3: Changes in Blood Lipids

Placebo represents the placebo control group, and Probiotics represents the probiotics experimental group. The changes in total cholesterol (CHOL) (A), triglycerides (TG) (B), high-density lipoprotein cholesterol (HDL) (C), and low-density lipoprotein cholesterol (LDL-C) (D) before and after sample consumption were calculated. No significant differences were observed between the two groups. In the probiotics group, 65% of participants showed a decrease in TG concentration, while the placebo group had a decrease rate of 18%.

[figure not shown]

Figure 4: Changes in Liver and Kidney Function

Placebo represents the placebo control group, and Probiotics represents the probiotics experimental group. The changes in liver function indicators, aspartate aminotransferase (AST) (A) and alanine aminotransferase (ALT) (B), as well as kidney function indicators, creatinine (CRE) (C) and blood urea nitrogen (BUN) (D), before and after sample consumption were calculated. No significant differences were observed between the two groups.

IRB/REC No. :	CMUH110-REC2-070
Page No. :	10/28

Table 2: Comparative Analysis of Blood Biochemical Indices Before and After the Experiment and Changes Before and After

Variables		Probiotics	Placebo	P-value ^b
		Mean \pm SEM	Mean \pm SEM	
ALT (U/L)	Pre	32.00 \pm 4.495	31.00 \pm 6.454	0.9897
	Post	28.12 \pm 4.853	37.69 \pm 7.946	0.7713
	Change	-3.882 \pm 3.461	6.692 \pm 6.747	0.5075
	P-value ^a	0.2462	0.3799	
AST (U/L)	Pre	24.31 \pm 1.886	22.38 \pm 3.054	0.3909
	Post	22.44 \pm 2.238	25.85 \pm 4.366	0.9053
	Change	-1.875 \pm 1.530	3.462 \pm 2.043	0.34

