	P-value ^a	0.0708	0.1367	
BUN (mg/dL)	Pre	13.82 \pm 0.6765	13.17 \pm 0.8242	0.9267
	Post	12.88 \pm 0.8985	12.67 \pm 0.7914	0.9694
	Change	-0.6250 \pm 0.7465	-0.5000 \pm 0.8118	>0.999
	P-value ^a	0.5256	0.6504	
CRE (mg/dL)	Pre	0.8241 \pm 0.03584	0.7962 \pm 0.0443	0.907
	Post	0.8775 \pm 0.04979	0.7915 \pm 0.04273	0.6543
	Change	0.0475 \pm 0.02713	-0.004615 \pm 0.02087	0.34
	P-value ^a	0.0535	0.8262	
CHOL (mg/dL)	Pre	200.7 \pm 10.33	186.9 \pm 11.49	0.67
	Post	204.6 \pm 12.42	186.3 \pm 10.20	0.0719
	Change	3.882 \pm 7.086	-0.6154 \pm 3.852	0.5075
	P-value ^a	0.6526	0.8535	
Glu-AC (mg/dL)	Pre	109.3 \pm 7.834	91.77 \pm 4.590	0.3871
	Post	100.7 \pm 9.383	91.69 \pm 6.466	0.5854
	Change	1.389 \pm 2.332	-0.07692 \pm 2.962	0.7803
	P-value ^a	0.6183	0.6846	
HbA1c (%)	Pre	6.124 \pm 0.2559	5.800 \pm 0.2295	0.8619
	Post	6.407 \pm 0.3149	5.931 \pm 0.3175	0.6367
	Change	0.2067 \pm 0.05893	0.1308 \pm 0.09765	0.4821
	P-value ^a	0.0029	0.2061	
HDL-C (mg/dL)	Pre	48.55 \pm 3.820	46.82 \pm 1.613	0.3643
	Post	47.38 \pm 3.125	46.43 \pm 1.798	0.4656
	Change	-0.0125 \pm 1.362	-0.3923 \pm 1.590	0.9872
	P-value ^a	0.4037	0.7227	
LDL-C (mg/dL)	Pre	113.0 \pm 7.399	122.8 \pm 12.17	0.4531
	Post	119.0 \pm 5.992	112.4 \pm 8.306	0.5874

IRB/REC No. :	CMUH110-REC2-070
Page No. :	11/28

	Change	6.012 ± 4.366	-12.04 ± 6.323	0.0946
	P-valuea	0.4586	0.0923	
TG (mg/dL)	Pre	220.9 ± 42.18	139.6 ± 14.47	0.5469
	Post	199.9 ± 40.46	177.4 ± 36.55	0.907
	Change	-21.00 ± 11.61	37.77 ± 34.12	0.0555
	P-valuea	0.1075	0.1577	

P-valuea **paired t-test (Pre and Post groups)**

P-valueb **unpaired t-test (Probiotics and Placebo groups)**

[figure not shown]

Figure 5: Changes in Lipids Carried by Serum Lipoproteins

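### Most between-group p-values in Table 2 are not the unpaired t-test that the footnote names; with that test the LDL-C change differs nominally against the probiotic

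*Combined protocol and SAP*

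**What the plan says.** The document describes the between-group test in three places, and they do not agree.

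- Methods and Design, last lines of Study Design and Intervention: "Statistical significance between groups were done by student paired t-test or Mann-Whitney test", followed by "P-values lower than 0.05 were considered statistically significant".
- Methods and Design, Data Analysis: "unpaired independent samples t-test, with significance set at" 0.05.
- Results, Table 2, footnote b: "unpaired t-test (Probiotics and Placebo groups". Footnote a labels the within-arm p-values as a paired t-test.

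No multiplicity rule is given for Table 2, and its rows carry no n. The Figure 3 legend, which covers CHOL, TG, HDL and LDL-C, says: "No significant differences were observed between the two groups. In the probiotics group, 65% of participants showed a decrease in TG concentration". The Figure 4 legend, which covers AST, ALT, CRE and BUN, says: "No significant differences were observed between the two groups".

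**The concern.** A p-value labelled with a t-test can be checked from two means and two SEMs. Here the check fails for most rows, by far more than rounding. Some values also repeat exactly across unrelated analytes: 0.5075 for the ALT and CHOL changes, 0.34 for the AST and CRE changes, and 0.907 for CRE pre and TG post. A t-test on continuous data would hardly ever do that. A statistic that can take only a limited set of values would.

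Two things are at stake. The main results table would be labelled with a test that was not run. And a conclusion may turn on the choice of test: the Background includes blood lipid levels in the primary goal, and LDL-C rose on the probiotic while it fell on placebo.

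**Working it through.** **Inputs.** Means and SEMs come from Table 2. The numbers randomised are stated: "Seventeen and 19 participants were respectively assigned to the placebo group and the probiotics group". The Table 1 row "Gender, male/female" gives 7 + 6 = 13 on placebo and 12 + 6 = 18 on probiotics. Because Table 2 prints no n, I ran every combination of 14 to 19 (probiotics) and 10 to 17 (placebo). For LDL-C, the Table 1 SD and the Table 2 SEM point to n = (42.15/12.17)² = 12.0 on placebo and (30.40/7.399)² = 16.9, so about 17, on probiotics. Tests are two-sided; the document does not state sidedness.

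**LDL-C change under the named test.** Difference = 6.012 − (−12.04) = +18.05 mg/dL.

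- Welch: SE = √(4.366² + 6.323²) = 7.68; t = 18.05/7.68 = 2.35. At 17 vs 12, p = 0.029 and the 95% CI is 2.1 to 34.0.
- Pooled, with SD = SEM × √n, so 18.0 and 21.9: SE = 7.42; t = 2.43 on 27 df. p = 0.022 and the 95% CI is 2.8 to 33.3.
- Over all n tried, p = 0.021 to 0.032. The printed 0.0946 is not reached.

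**Other rows**, pooled and Welch over the same grid:

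| Row | Printed p | Unpaired t-test p |
|---|---|---|
| AST change | 0.34 | 0.041–0.053 |
| ALT change | 0.5075 | 0.13–0.20 |
| ALT post | 0.7713 | 0.28–0.34 |
| CRE post | 0.6543 | 0.20–0.27 |
| CHOL post | 0.0719 | 0.26–0.34 |
| TG change | 0.0555 | 0.054–0.144 |
| HbA1c change | 0.4821 | 0.484–0.533 |

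Of the 30 between-group rows, 28 lie outside the t-test range by more than 0.005. The exceptions are TG change, which is inside it, and HbA1c change, which misses by 0.002. At TG's likely n of 17 vs 13, the t-test gives 0.082 (pooled) or 0.124 (Welch).

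**What reproduces the printed values.** The asymptotic two-sample Kolmogorov-Smirnov formula is p = 2Σ(−1)^(k−1) exp(−2k²λ²), with λ = D√(n₁n₂/(n₁+n₂)).

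- LDL-C change at 17 vs 12, D = 95/204: λ = 0.4657 × 2.652 = 1.235; p = 2 exp(−3.051) = 0.0946.
- AST and CRE changes at 16 vs 13, D = 73/208: λ = 0.940; p = 0.3417 − 0.0017 = 0.3400.

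Every numeric between-group p-value in Table 2 is matched to the printed precision at n of 15 to 18 vs 12 to 13. The BUN change, printed only as >0.999, cannot be tested this way. Exact Mann-Whitney matches almost none.

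**Footnote a (paired).** t = mean change / SEM.

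- AST, probiotics: −1.875/1.530 = −1.23, p about 0.24; printed 0.0708.
- LDL-C, probiotics: 6.012/4.366 = 1.38, p about 0.19; printed 0.4586.

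**Change against Post minus Pre.**

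- LDL-C, placebo: 112.4 − 122.8 = −10.4; printed −12.04.
- HDL-C, probiotics: 47.38 − 48.55 = −1.17; printed −0.0125.
- Glu-AC, probiotics: 100.7 − 109.3 = −8.6; printed +1.389.

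With −10.4 and the same SEM, the LDL-C difference is 6.012 + 10.4 = +16.4 mg/dL. At 17 vs 12, p = 0.036 (pooled) or 0.045 (Welch); over the whole grid it is 0.035 to 0.050.

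**The case against.** The strongest reply is that Methods also allows a Mann-Whitney test and gives no rule for choosing. A Mann-Whitney p-value for LDL-C cannot be computed without individual data, so a non-significant result under that test is possible. This stands. A reader might infer that the Figure 3 statement has been proved false or that the probiotic has been shown to raise LDL-C. The documents do not support either. They show only that the statement is unsupported by the test that Data Analysis and footnote b name. The reply does not rescue the label: the footnote does not claim Mann-Whitney, and the printed values do not fit it.

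Second, the recalculation trusts means and SEMs from a table whose Change means disagree with its own Pre and Post means. Different numbers of patients per row may explain that, but no n is printed to show it. The LDL-C result then moves closer to 0.05, though it stays below at the likely n.

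Third, the HDL-C probiotics row looks like a glaring paired-test error (−0.0125/1.362 gives p about 0.99 against 0.4037 printed). It is ambiguous: −1.17/1.362 gives 0.4038 at n = 16, so the faulty entry may be the Change mean. I do not rely on it.

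Fourth, the legends do agree with the p-values as printed. The fault lies in those p-values and their label.

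**Conclusion.** The label on the between-group column is wrong for most rows, and several within-arm p-values do not fit their label either. The two Methods statements also conflict. That the software ran a Kolmogorov-Smirnov test is an inference from the close match; the document does not say so.

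Under the named test and threshold, the LDL-C change differs nominally against the probiotic by about 18 mg/dL (95% CI about 2 to 34), or about 16 if the placebo change is −10.4. About two thirds of the difference (12.04 of 18.05) is the fall on placebo. The AST change is −1.875 − 3.462 = −5.3 U/L in the probiotic's favour. It is borderline: p = 0.042 (pooled) or 0.048 (Welch) at 16 vs 13, and 0.041 to 0.053 over the grid. Neither result would pass a correction over ten analytes, where the smallest p must fall below 0.05/10 = 0.005.

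The mismatches run in both directions: CHOL post is printed smaller than the t-test gives, LDL-C change larger. A reader might infer that the test was chosen to hide an adverse lipid result. Nothing in the documents shows that, and the AST row would have helped the probiotic. All sizes here assume two-sided tests and that the printed Change means and SEMs are right.

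**What to change.** 1. Settle on one between-group test, and make the Study Design paragraph, Data Analysis and footnote b agree on it.
2. Rerun both p-value columns of Table 2 from source data with the named tests.
3. Print n per arm in every row, and the 95% CI of the between-group difference in change.
4. Reconcile the Change means with Pre and Post for LDL-C placebo, HDL-C probiotics and Glu-AC probiotics, or explain them by the n.
5. Correct footnotes a and b.
6. Restate the Figure 3 and Figure 4 legends from the rerun, not from this recalculation. Report any LDL-C or AST difference as nominal and unadjusted for multiplicity.

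The cost is ten small reanalyses and some text. The downside for the sponsor is probably a less favourable LDL-C statement; the AST statement may move the other way.

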Placebo represents the placebo control group, and Probiotics represents the probiotics experimental group. Individual comparisons of changes in lipids carried by serum lipoproteins before and after sample consumption are depicted. The size of the points in the scatter plot ($-\log_{10}$ p values) and the color (log2 fold change denoted as log2FC, with red indicating positive correlation changes and blue indicating negative correlation changes) are used to distinguish between inter-group differences and trends. Serum very low-density lipoprotein (VLDL), low-density lipoprotein (LDL), and high-density lipoprotein (HDL) have the ability to carry cholesterol (Chol), lipids, cholesterol esters (CE), and triglycerides (TG) individually. The experimental data indicate that probiotics upregulate the content of

IRB/REC No. :	CMUH110-REC2-070
Page No. :	13/28

lipids carried by HDL (Chol:Lipid and CE:Lipid). Simultaneously, there is a significant decrease in the total amount of lipids carried by VLDL (L-VLDL, XL-VLDL, XXL-VLDL). Additionally, there is a significant decrease in triglycerides (TG) carried by both VLDL and HDL.

IRB/REC No. :	CMUH110-REC2-070
Page No. :	14/28

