L-HDL-FC %	Free cholesterol to total lipids ratio in large HDL	%
L-HDL-TG %	Triglycerides to total lipids ratio in large HDL	%
M-HDL-PL %	Phospholipids to total lipids ratio in medium HDL	%
M-HDL-C %	Cholesterol to total lipids ratio in medium HDL	%
M-HDL-CE %	Cholesteryl esters to total lipids ratio in medium HDL	%
M-HDL-FC %	Free cholesterol to total lipids ratio in medium HDL	%
M-HDL-TG %	Triglycerides to total lipids ratio in medium HDL	%
S-HDL-PL %	Phospholipids to total lipids ratio in small HDL	%
S-HDL-C %	Cholesterol to total lipids ratio in small HDL	%
S-HDL-CE %	Cholesteryl esters to total lipids ratio in small HDL	%
S-HDL-FC %	Free cholesterol to total lipids ratio in small HDL	%
S-HDL-TG %	Triglycerides to total lipids ratio in small HDL	%

IRB/REC No. :	CMUH110-REC2-070
Page No. :	20/28

Table 4: Comparative Analysis of Metabolomic Pre-test and Post-test Results for Placebo Group Blood Samples

Differential expression analysis								
Significance(p-value)	Feature	Mean(after)	Mean(before)	Method	FC	Log2(FC)	-Log10(p-value)	-Log10(padj)
yes	Creatinine	64.21	59.285	t-test	0.923	-0.115	2.023	0.103
yes	IDL_CE_pct	51.149	49.621	t-test	0.97	-0.044	2.623	0.527
yes	IDL_C_pct	67.73	66.121	t-test	0.976	-0.035	2.767	0.527
yes	IDL_TG_pct	8.787	10.075	t-test	1.147	0.197	1.332	0.06
yes	L_LDL_CE_pct	53.99	53.463	t-test	0.99	-0.014	1.562	0.06
yes	L_LDL_C_pct	71.967	71.136	t-test	0.988	-0.017	1.59	0.06
yes	L_LDL_TG_pct	5.966	6.83	t-test	1.145	0.195	1.397	0.06
yes	M_LDL_PL_pct	26.658	26.309	t-test	0.987	-0.019	1.452	0.06
no	Acetate	0.017	0.019	t-test	1.092	0.126	0.309	0.06
no	Acetoacetate	0.025	0.019	t-test	0.741	-0.432	0.366	0.06
no	Acetone	0.019	0.021	t-test	1.063	0.089	0.067	0.005
no	Ala	0.337	0.383	t-test	1.137	0.185	1.234	0.06
no	Albumin	41.434	40.602	t-test	0.98	-0.029	0.259	0.06
no	ApoA1	1.416	1.353	t-test	0.955	-0.066	0.477	0.06
no	ApoB	0.878	0.858	t-test	0.977	-0.033	0.24	0.06
no	ApoB_by_ApoA1	0.63	0.642	t-test	1.019	0.027	0.179	0.027
no	bOHbutyrate	0.094	0.103	t-test	1.1	0.137	0.063	0.005
no	Cholines	2.554	2.454	t-test	0.961	-0.058	0.361	0.06
no	Citrate	0.06	0.063	t-test	1.043	0.061	1.126	0.06
no	Clinical_LDL_C	2.787	2.6	t-test	0.933	-0.101	0.605	0.06
no	DHA	0.323	0.291	t-test	0.9	-0.152	0.271	0.06
no	DHA_pct	2.574	2.387	t-test	0.927	-0.109	0.292	0.06
no	Gln	0.487	0.495	t-test	1.016	0.022	0.099	0.005
no	Glucose	4.525	3.994	t-test	0.883	-0.18	0.749	0.06
no	Gly	0.251	0.302	t-test	1.202	0.265	1.129	0.06
no	GlycA	0.857	0.83	t-test	0.968	-0.046	0.294	0.06

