no	Glycerol	0.106	0.121	t-test	1.149	0.2	0.283	0.06
no	HDL_C	1.273	1.184	t-test	0.93	-0.105	0.665	0.06
no	HDL_CE	1.006	0.931	t-test	0.925	-0.113	0.733	0.06
no	HDL_FC	0.267	0.253	t-test	0.948	-0.077	0.401	0.06
no	HDL_L	2.818	2.668	t-test	0.947	-0.079	0.466	0.06
no	HDL_P	0.016	0.015	t-test	0.945	-0.081	0.57	0.06
no	HDL_PL	1.426	1.356	t-test	0.951	-0.072	0.403	0.06
no	HDL_size	9.47	9.463	t-test	0.999	-0.001	0.142	0.01
no	HDL_TG	0.119	0.128	t-test	1.082	0.113	0.309	0.06
no	His	0.07	0.071	t-test	1.014	0.02	0.056	0.005
no	IDL_C	0.779	0.726	t-test	0.932	-0.101	0.697	0.06
no	IDL_CE	0.588	0.544	t-test	0.925	-0.112	0.755	0.06
no	IDL_FC	0.191	0.182	t-test	0.954	-0.068	0.432	0.06
no	IDL_FC_pct	16.581	16.5	t-test	0.995	-0.007	0.103	0.005
no	IDL_L	1.143	1.094	t-test	0.957	-0.063	0.413	0.06
no	IDL_P	0	0	t-test	0.959	-0.06	0.51	0.06
no	IDL_PL	0.268	0.261	t-test	0.973	-0.039	0.233	0.06
no	IDL_PL_pct	23.483	23.804	t-test	1.014	0.02	0.531	0.06

IRB/REC No. :	CMUH110-REC2-070
Page No. :	21/28

no	IDL_TG	0.095	0.106	t-test	1.116	0.159	0.904	0.06
no	Ile	0.058	0.07	t-test	1.196	0.258	0.728	0.06
no	LA	4.198	4.005	t-test	0.954	-0.068	0.447	0.06
no	Lactate	2.987	4.773	t-test	1.598	0.676	0.666	0.06
no	LA_pct	33.798	33.094	t-test	0.979	-0.03	0.269	0.06
no	LDL_C	1.974	1.859	t-test	0.942	-0.087	0.562	0.06
no	LDL_CE	1.458	1.378	t-test	0.945	-0.082	0.526	0.06
no	LDL_FC	0.516	0.481	t-test	0.932	-0.102	0.64	0.06
no	LDL_L	2.805	2.671	t-test	0.952	-0.07	0.455	0.06
no	LDL_P	0.001	0.001	t-test	0.977	-0.034	0.233	0.06
no	LDL_PL	0.679	0.646	t-test	0.952	-0.072	0.489	0.06
no	LDL_size	23.873	23.877	t-test	1	0	0.06	0.005
no	LDL_TG	0.151	0.166	t-test	1.097	0.133	0.715	0.06
no	Leu	0.128	0.147	t-test	1.145	0.196	0.541	0.06
no	L_HDL_C	0.21	0.186	t-test	0.884	-0.178	0.729	0.06
no	L_HDL_CE	0.168	0.147	t-test	0.876	-0.191	0.809	0.06
no	L_HDL_CE_pct	35.405	31.348	t-test	0.885	-0.176	0.669	0.06
no	L_HDL_C_pct	43.805	39.532	t-test	0.902	-0.148	0.641	0.06
no	L_HDL_FC	0.043	0.039	t-test	0.916	-0.126	0.386	0.06
no	L_HDL_FC_pct	8.4	8.184	t-test	0.974	-0.038	0.283	0.06
no	L_HDL_L	0.46	0.416	t-test	0.905	-0.144	0.532	0.06
no	L_HDL_P	0.001	0.001	t-test	0.894	-0.162	0.631	0.06
no	L_HDL_PL	0.231	0.21	t-test	0.908	-0.139	0.448	0.06
no	L_HDL_PL_pct	51.036	52.628	t-test	1.031	0.044	0.609	0.06
no	L_HDL_TG	0.018	0.02	t-test	1.111	0.151	0.24	0.06
no	L_HDL_TG_pct	5.159	7.841	t-test	1.52	0.604	0.624	0.06
no	L_LDL_C	1.258	1.172	t-test	0.932	-0.101	0.64	0.06
no	L_LDL_CE	0.943	0.88	t-test	0.933	-0.1	0.626	0.06

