no	XXL_VLDL_P	0	0	t-test	0.992	-0.012	0.01	0.002
no	XXL_VLDL_PL	0.026	0.026	t-test	0.986	-0.021	0.017	0.002
no	XXL_VLDL_PL_pct	14.889	16.636	t-test	1.117	0.16	0.527	0.06
no	XXL_VLDL_TG	0.084	0.074	t-test	0.879	-0.187	0.136	0.01
no	XXL_VLDL_TG_pct	34.697	43.814	t-test	1.263	0.337	0.413	0.06

IRB/REC No. :	CMUH110-REC2-070
Page No. :	25/28

Table 5: Comparative Analysis of Metabolomic Pre-test and Post-test Results for Probiotics Group Blood Samples

Differential expression analysis								
Significance(p-value)	Feature	Mean(after)	Mean(before)	Method	FC	Log2(FC)	-Log10(p-value)	-Log10(padj)
yes	Acetate	0.017	0.019	t-test	1.156	0.209	1.329	0.407
yes	Gly	0.263	0.295	t-test	1.123	0.167	1.447	0.407
yes	HDL_size	9.573	9.508	t-test	0.993	-0.01	1.433	0.407
yes	Lactate	4.175	5.984	t-test	1.433	0.519	1.441	0.407
yes	L_VLDL_CE_pct	14.036	15.354	t-test	1.094	0.129	1.363	0.407
yes	L_VLDL_C_pct	28.119	29.999	t-test	1.067	0.093	1.505	0.407
yes	L_VLDL_FC_pct	14.083	14.645	t-test	1.04	0.056	1.643	0.421
yes	L_VLDL_L	0.563	0.48	t-test	0.853	-0.229	1.334	0.407
yes	L_VLDL_TG	0.288	0.233	t-test	0.81	-0.304	2.037	0.533
yes	L_VLDL_TG_pct	51.128	49.056	t-test	0.959	-0.06	1.429	0.407
yes	M_HDL_CE_pct	37.7	39.269	t-test	1.042	0.059	2.902	0.805
yes	M_HDL_C_pct	46.11	47.515	t-test	1.03	0.043	3.121	0.805
yes	M_HDL_PL_pct	47.018	46.34	t-test	0.986	-0.021	1.977	0.533
yes	M_HDL_TG_pct	6.873	6.145	t-test	0.894	-0.161	1.715	0.463
yes	M_VLDL_PL_pct	21.414	22.043	t-test	1.029	0.042	1.319	0.407
yes	S_HDL_CE_pct	27.533	28.901	t-test	1.05	0.07	1.987	0.533
yes	S_HDL_C_pct	37.973	39.337	t-test	1.036	0.051	2.162	0.533
yes	S_HDL_PL_pct	55.964	55.036	t-test	0.983	-0.024	1.839	0.52
yes	S_HDL_TG_pct	6.063	5.628	t-test	0.928	-0.107	1.571	0.407
yes	S_LDL_C_pct	62.862	63.718	t-test	1.014	0.019	2.566	0.645
yes	TG_by_PG	0.778	0.696	t-test	0.895	-0.161	1.792	0.508
yes	VLDL_size	39.666	39.173	t-test	0.988	-0.018	2.006	0.533
yes	VLDL_TG	1.623	1.384	t-test	0.853	-0.229	1.355	0.407
yes	XL_HDL_CE_pct	36.249	38.447	t-test	1.061	0.085	1.922	0.524
yes	XL_HDL_C_pct	52.182	56.422	t-test	1.081	0.113	1.345	0.407
yes	XL_VLDL_L	0.381	0.323	t-test	0.847	-0.239	1.334	0.407
yes	XL_VLDL_TG	0.221	0.181	t-test	0.818	-0.291	1.843	0.52
yes	XXL_VLDL_L	0.467	0.375	t-test	0.804	-0.315	1.494	0.407
yes	XXL_VLDL_P	0	0	t-test	0.817	-0.292	1.395	0.407
yes	XXL_VLDL_TG	0.267	0.202	t-test	0.756	-0.403	2.073	0.533
no	Acetoacetate	0.026	0.017	t-test	0.651	-0.619	0.697	0.243
no	Acetone	0.016	0.02	t-test	1.238	0.308	0.6	0.219

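### The lipid changes that Figure 5 credits to the probiotic are documented only by separate before-after tests within each arm, so a treatment effect is not shown

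*Combined protocol and SAP*

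**What the plan says.** The legend of Figure 5 (Results) makes the document's only favourable statements that are called significant or put as an established effect. It says "The experimental data indicate that probiotics upregulate the content of" lipids carried by HDL (the cholesterol and cholesteryl ester shares), that "there is a significant decrease in the total amount of lipids carried by VLDL" in the large, very large and extremely large classes, and that triglycerides in VLDL and HDL also fell significantly.

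The supporting tests are in the Appendix. Table 4 is titled "Comparative Analysis of Metabolomic Pre-test and Post-test Results for Placebo Group Blood Samples" and Table 5 "Comparative Analysis of Metabolomic Pre-test and Post-test Results for Probiotics Group Blood Samples". Each is a pre-post analysis of one arm. Table 4 flags 8 features as significant and Table 5 flags 30.

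The methods text is not consistent. The end of Study Design and Intervention says "Statistical significance between groups were done by student paired t-test or Mann-Whitney test" and "P-values lower than 0.05 were considered statistically significant". Data Analysis says "The statistical analysis was conducted using GraphPad's unpaired independent samples t-test". Table 2 does print between-arm p-values for the clinical laboratory values, and the legends of Figures 1 to 4 report no significant differences between the groups.

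**The concern.** A pre-post test within one arm responds to anything that changes between day 1 and day 84: drift, sample handling, diet, and regression to the mean, as well as the product. The placebo arm is there to remove these, and it does so only if the two changes are compared directly. A p-value below 0.05 in one arm and above 0.05 in the other is not that comparison.

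Regression to the mean is a live possibility here. Baseline triglycerides in Table 1 are 220.94 mg/dL on probiotics and 139.62 mg/dL on placebo, so some fall in the higher arm could occur with no treatment effect.

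At stake is the one positive conclusion of a trial whose weight, glucose and clinical lipid comparisons are reported as null.

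**Working it through.** **Figures that need no reconstruction.** The printed columns are −log10 values.

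- The largest −log10 adjusted p in Table 5 is 0.805, and 10^−0.805 = 0.157. To reproduce it by the Benjamini-Hochberg method, assume 250 features (the count is not stated). The two smallest raw p-values are 10^−3.121 = 0.00076 and 10^−2.902 = 0.00125. Then 0.00125 × 250 / 2 = 0.157, as printed. The significance flags therefore use raw p < 0.05, and no feature survives the document's own adjustment.
- HDL triglyceride concentration in the probiotics arm: 10^−0.361 = 0.44. It is not significant even within the arm, so the HDL triglyceride wording can rest only on the percentage rows for medium and small HDL.
- Lactate shows how the method fails. It is flagged in probiotics (4.175 and 5.984, a difference of 1.81). The placebo row reads "Lactate 2.987 4.773 t-test 1.598", a difference of 1.79, and is not flagged.

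**Column labels.** In both tables FC is the column headed before divided by the column headed after. For probiotics VLDL_TG, 1.384 / 1.623 = 0.853. As labelled, VLDL_TG rose from 1.384 to 1.623, yet the legend reports a fall. Table 2 triglycerides on probiotics fell (220.9 to 199.9) and LDL-C rose (113.0 to 119.0), which fits swapped headers. Creatinine points the other way: it rose in Table 2 (0.8241 to 0.8775) and also rises in Table 5 as labelled (68.671 to 72.354). I treat the headers as swapped. If both tables carry the same error, this sets the sign of the differences and not the two-sided p-values.

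**Approximate between-arm tests.** Assumptions:

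- The within-arm tests are paired. Table 1 gives a triglyceride SD/mean of 173.92/220.94 = 0.79, so an unpaired SE would be about 0.79 × √(2/17) = 27% of the mean. The SE implied by the Total_TG row of Table 5 is 0.142/2.227 = 6%.
- The metabolomic n is not stated. (SD/SEM)² for triglycerides in Tables 1 and 2 gives (173.92/42.18)² = 17 and (52.18/14.47)² = 13. I varied n from 14 and 10 to 19 and 17.

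For each arm, change d = first mean × (2^log2FC − 1), and SE = |d| / t, where t is the quantile matching the printed p on n − 1 df. The arms are then compared by a Welch test on d₁ − d₀.

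Example, VLDL_TG with n = 17 and 13:

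- Probiotics: p = 10^−1.355 = 0.044, t = 2.184, d = −0.238, SE = 0.109.
- Placebo: p = 10^−0.018 = 0.959, t = 0.052, d = −0.006, SE = 0.116.
- Difference −0.232, SE = √(0.109² + 0.116²) = 0.160, t = −1.46 on about 27 df, p = 0.16. The 95% interval is about −0.56 to 0.10 mmol/l.

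The table gives d (SE) at n = 17 and 13. The p range covers the values of n above and both ways of getting d (from log2FC or from the printed means).

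| Feature | Probiotics | Placebo | Between-arm p |
|---|---|---|---|
| L-VLDL lipids | −0.083 (0.038) | −0.002 (0.039) | 0.15 |
| XL-VLDL lipids | −0.058 (0.027) | 0.005 (0.028) | 0.09–0.12 |
| XXL-VLDL lipids | −0.092 (0.039) | −0.007 (0.045) | 0.17–0.18 |
| VLDL-TG | −0.238 (0.109) | −0.006 (0.116) | 0.15–0.16 |
| L-VLDL-TG | −0.055 (0.019) | −0.005 (0.025) | 0.08–0.12 |
| XL-VLDL-TG | −0.040 (0.015) | 0.003 (0.019) | 0.06–0.08 |
| XXL-VLDL-TG | −0.065 (0.022) | −0.010 (0.029) | 0.14 |
| HDL-TG concentration | −0.013 (0.016) | 0.010 (0.014) | 0.29 |
| M-HDL cholesterol share, % | 1.40 (0.34) | −0.85 (0.87) | 0.03 |
| S-HDL cholesterol share, % | 1.37 (0.44) | −0.50 (0.51) | 0.01 |
| M-HDL TG share, % | −0.73 (0.28) | 0.58 (0.55) | 0.05 |
| S-HDL TG share, % | −0.43 (0.18) | 0.44 (0.32) | 0.03 |

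The cholesteryl ester shares give about 0.02 (M-HDL) and 0.01 (S-HDL). The XL-HDL cholesterol and ester shares, both flagged in Table 5, give about 0.18 and 0.14. Lactate gives 0.99.

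The placebo SEs divide a near-zero change by a near-zero t, so rounding matters. For XL-VLDL-TG, the row nearest to 0.05, the log2FC route is the less rounded one and gives 0.08.

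**The case against.** Figure 5 itself is not available in the text, and its legend says that point size and colour mark differences between the groups. A between-arm test may lie behind it. That cannot be excluded, but nothing tabulated supports it, and the same legend describes changes before and after consumption.

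Some of the HDL claims fare better than the VLDL claims. The medium and small HDL cholesterol, ester and triglyceride shares stay nominally below 0.05 between arms. This stands, before multiplicity correction.

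The reconstruction uses rounded figures, an assumed n and unadjusted changes on the raw scale. It cannot predict what a baseline-adjusted model on the log scale would give. This also stands.

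Four stronger readings are tempting, and the documents do not support them:

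- That the trial left its randomised control unused. Table 2 and Figures 1 to 4 compare the arms; the defect is confined to the metabolomic analysis.
- That the lipid claims are false. The VLDL-TG interval above still contains a sizeable fall.
- That the legend credits the product with every flagged feature. It does not name lactate, for example, so that row illustrates the method's weakness and rebuts no claim.
- That the within-arm HbA1c rise on probiotics (0.2067, p = 0.0029) was hidden. Table 2 prints it with its between-arm p of 0.4821, and Figure 2 reports the between-arm result. It does show that HbA1c was judged between arms while the metabolomic lipids were judged within them.

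**Conclusion.** The concern holds for the metabolomic analysis. The falls in VLDL lipids and VLDL triglycerides are not shown to be treatment effects: no between-arm test is documented, no within-arm result survives the printed adjustment (smallest adjusted p 0.157), and the approximate between-arm p-values run from 0.06 to 0.18. The fall in HDL triglyceride concentration is not supported even within the arm (p = 0.44; about 0.29 between arms). The changes in medium and small HDL composition are at most nominal, about 0.01 to 0.05 uncorrected, and should be called exploratory.

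The printed within-arm p-values need no assumption. The between-arm values rest on paired tests, an n of 14 to 19 and 10 to 17, and rounded input. The direction of every change rests on the headers being swapped. The analysis should be corrected before the legend's conclusions are relied on.

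**What to change.** 1. Reconcile the before/after headers of Tables 4 and 5 with FC, the legend and Table 2, working from the raw data.
2. Make the two statements of the statistical test agree.
3. Replace the tests in Tables 4 and 5 with one table. For each feature, regress the day-84 value (log scale for concentrations) on arm and baseline. Report n per arm, the between-arm difference, its 95% confidence interval and an FDR-adjusted p. State how many features were tested. Baseline adjustment matters because the arms start far apart on triglycerides.
4. Base every statement about the probiotic on that table. Keep within-arm changes as description, without p-values, and label Figure 5 exploratory.
5. Withdraw any sentence claiming a significant decrease or an upregulation that the between-arm result does not support. If a between-arm test already lies behind Figure 5, print it.

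The cost is some reanalysis of data already held. The downside for the sponsor is a weaker headline lipid claim.
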